Data Analysis: We will obtain descriptive information on primary and secondary outcomes. In particular, at each time-point, we will obtain the mean, median, SD, and range for each measure and for the changes from baseline for each measure, for the MitoQ and placebo subject groups. We will also obtain 95% confidence intervals for the changes from baseline for each measure, at each time point for both subject groups. We will conduct a t-test to compare primary and secondary measures (changes from baseline) and to obtain the associated 95% confidence intervals for the differences in mean change between the MitoQ and placebo subject groups. We will focus on the confidence intervals that describe the plausible differences in mean change between the subject groups. These confidence intervals will provide information about the magnitude of differences in MFIS and FSS changes between subject groups that are consistent with the previous data. We will also test for differences in the change scores by group in a linear regression framework, adjusting for demographic and clinical characteristics, such as gender. As a secondary analysis, we will use an ANCOVA test with 12-week MFIS score as the outcome and baseline MFIS score as a covariate to account for baseline differences in fatigue among patients. We will use a linear mixed model to analyze MFIS changes over time with fixed effects for time, incorporating baseline values of the outcome as a covariate, and random intercepts and slopes for individuals to incorporate within-subject variability. Due to the exploratory nature of this study, the 6 week time point will provide evidence of whether or not change is seen by 6 weeks. It will allow us to understand how long MitoQ takes to have an effect, and this information will be useful for planning future studies. Both formal hypothesis testing and confidence interval estimation will be conducted. To detect a trend in the effect of MitoQ dosage, we will perform an ANOVA trend analysis on the change in MFIS between baseline and 12 weeks among the three treatment groups. In addition, we will categorize participants who improved by a reliable change, defined as differences in group means divided by the standard error, greater than 1.96 points and test for differences in the proportion of improvers by group using a chi-squared test. The standard error is given by $s_1\sqrt{1 - r_{xx}}$, where s_1 is the standard deviation of the control group and r_{xx} is the MFIS test-retest reliability (here, given by the MFIS Cronbach's alpha value of 0.81.⁶ This analysis will yield additional power (compared to a 2-sample t-test) and will provide useful data for planning a repeated measures analysis in a future larger trial. Secondary outcomes will be analyzed in the same manner. To test if the effect of MitoQ on FSS depended on compliance, compliance (as measured by pill counting) will be treated as a co-variate in the analyses. Patterns of missing data will be examined to determine if patient characteristics are related to missing follow-up data. Statistical significance is defined as $P < 0.05$. SPSS for Windows Version 15.0 (SPSS Inc., Chicago) and SAS (SAS Institute, Cary, NC) will be used for analysis.

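### The MFIS reliable-change rule is built on a difference in group means, so it cannot label any participant an improver; read as individual change, its standard error is that of one score, not of a change

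*Combined protocol and SAP*

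**What the plan says.** In Specific Aim 1, Statistical Analysis, the Data Analysis paragraph adds a responder analysis to the comparisons of mean MFIS change:

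- The aim is individual classification: "we will categorize participants who improved by a reliable change".
- The criterion is "defined as differences in group means divided by the standard error, greater than 1.96 points".
- The standard error is s_1√(1 − r_xx), "where s_1 is the standard deviation of the control group". The plan does not say whether that is an SD of single scores or of changes, or at which visit.
- r_xx "is the MFIS test-retest reliability (here, given by the MFIS" Cronbach's alpha of 0.81.
- The resulting labels are used to "test for differences in the proportion of improvers by group using a chi-squared test".

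Specific Aim 1, Procedures, defines the primary outcome as the change in total MFIS from baseline to 12 weeks. It gives no responder threshold, and no other section supplies an individual-level rule.

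**The concern.** The stated purpose and the stated statistic do not match. Labelling participants needs a quantity that differs between participants, and a difference in group means does not. Followed literally, the rule gives a single yes or no for each comparison of arms.

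An analyst would almost certainly substitute each participant's own change. That exposes a second problem. The expression s_1√(1 − r_xx), with s_1 a single-score SD, is the measurement error of one score. A change is the difference of two scores and carries the error of both, so the cut-off would be too low for the 1.96 criterion to mean what it usually means.

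At stake are the reported percentages of improvers in every arm, which readers may take as the proportion with real change and which may be carried into planning the later trial. If the rule is settled only at analysis, the analyst must also choose the numerator and the meaning of s_1 at that point, which pre-specification is meant to prevent.

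**Working it through.** The plan states no cut-off in points, no misclassification rate and no sample size for this analysis, so there is no figure of its own to reproduce.

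**Inputs from the plan:** criterion 1.96; r_xx = 0.81; standard error s_1√(1 − r_xx). **Assumptions:** normal errors with equal variance at both visits; MFIS SD, true retest reliability, arm sizes, treatment shift and baseline to week-12 correlation as given below.

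**1. The rule as written.** The condition is (difference in group means) / (s_1√0.19) > 1.96, that is, a mean difference above 1.96 × 0.4359 s_1 = 0.854 s_1. Nothing in it is indexed by participant. The chi-squared table of improvers by arm cannot be filled.

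**2. Individual change, s_1 a single-score SD.** Each score has error variance s_1²(1 − r), so a difference of two has error SD s_1√(2(1 − r)).

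- Plan: SE = √0.19 s_1 = 0.436 s_1; cut-off 1.96 × 0.4359 = 0.854 s_1.
- Change score: SE = √0.38 s_1 = 0.616 s_1; cut-off 1.96 × 0.6164 = 1.208 s_1.

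| Assumed MFIS SD | Plan's cut-off (points) | With √2 (points) |
|---|---|---|
| 10 | 8.5 | 12.1 |
| 15 | 12.8 | 18.1 |
| 20 | 17.1 | 24.2 |

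**3. False improvers.** For a participant with no true change and true retest reliability r, the rate is P(Z > cut-off / √(2(1 − r))), with the cut-off in units of s_1.

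| True retest r | Plan's cut-off (0.854) | Cut-off with √2 (1.208) |
|---|---|---|
| 0.60 | 17.0% | 8.8% |
| 0.70 | 13.5% | 5.9% |
| 0.81 | 8.3% | 2.5% |
| 0.90 | 2.8% | 0.3% |

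At r = 0.81 the plan's rule is really a cut at Z = 1.96/√2 = 1.386. It meets the 2.5% implied by 1.96 only when 2(1 − r) = 0.19, that is r = 0.905. Above that it is too strict (0.3% at r = 0.95).

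**4. Individual change, s_1 an SD of change.** Then √(1 − r_xx) has no place in the formula. If all change is noise, the rate is P(Z > 0.854) = 19.6%. This reading does not rescue the rule.

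**5. Effect on the chi-squared test.** This was simulated with normal scores, s_1 the placebo baseline SD, pooled MitoQ against placebo, a two-sided 5% test and a baseline to week-12 correlation of 0.6. With no treatment effect and 10, 20 or 30 per arm, the test with the plan's cut-off rejects in 4.0%, 4.7% and 5.2% of trials. Too low a cut-off raises the improver count in all arms alike, so type I error is not materially inflated.

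**The case against.** The strongest reply is that this is a drafting slip in one clause. The same sentence speaks of participants who improved and of a proportion of improvers, and Procedures defines the outcome as change from baseline to week 12. Any analyst would infer an individual numerator. That is fair as to intent, but the rule as written still cannot produce the analysis, and inferring the numerator leaves the standard error unsettled.

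A second reply is that the missing √2 is certain only if s_1 is a single-score SD, which the plan does not say. This stands, and the point is made only on that condition. The alternative reading gives 19.6%, so it offers no escape.

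Third, 2.5% is implied by 1.96 and is not a stated target, and 0.81 is a Cronbach's alpha openly used in place of a test-retest value. If true retest reliability were near 0.90, the plan's cut-off would be almost on target; if it were 0.60 to 0.70, the corrected one would still be too lenient. This also stands. Adding √2 makes the formula right for a change score but does not make 0.81 the right reliability.

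Finally, the analysis is supportive in an exploratory pilot whose emphasis is on confidence intervals. That limits the weight of the point.

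**Conclusion.** The concern holds. That the rule cannot classify individuals follows from the text alone and needs no assumption. The standard-error fault holds if s_1 is a single-score SD: the cut-off is then 0.854 s_1 where 1.208 s_1 is needed, and 8.3% of unchanged participants are called improved instead of 2.5%, given normal errors and a true retest reliability of 0.81. The size and even the direction of the misclassification depend on that reliability, with break-even at 0.905.

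The damage is confined to the responder percentages. The primary t-test, ANCOVA, mixed model and dose trend do not use this rule, and the chi-squared test's type I error is not materially inflated. It should be corrected before analysis, as a minor to moderate point.

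**What to change.** Replace the definition with, for example: *An improver is a participant whose own fall in total MFIS from baseline to week 12, divided by s_1√(2(1 − r)), exceeds 1.96, where s_1 is the placebo-arm SD of baseline MFIS and r = 0.81.* This takes a lower score as less fatigue. Drop the word points, since the criterion is a ratio, and label the analysis supportive.

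The same edit should settle four details:

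- **Baseline visit.** Table 2 marks MFIS at both Visit 1 and Visit 2, while the Overall Design table lists times 0, 6 and 12 weeks. Reconcile these and name the visit used. If MFIS is collected at both, the Visit 1 to Visit 2 correlation can serve as r in a sensitivity analysis. It spans one week and is imprecise: an observed 0.81 from an assumed 60 participants has a 95% CI of 0.70 to 0.88.
- **Arms compared.** The t-test is "for the differences in mean change between the MitoQ and placebo subject groups", while the dose trend is "among the three treatment groups". Say which the chi-squared test uses.
- **Missing week-12 scores.** The only provision is "Patterns of missing data will be examined to determine if patient characteristics are related to missing follow-up data". State how such a participant is classified, for example as not improved, with a completers-only sensitivity analysis.
- **Other measures.** Apply the rule to MFIS only, unless a reliability is given for each other scale.

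The main rule costs only SAP wording and needs no new data. Its statistical price, under an assumed 0.6 SD shift and correlation of 0.6, is:

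| Placebo v pooled MitoQ | Chi-squared power, plan's cut-off | Chi-squared power, corrected |
|---|---|---|
| 10 v 20 | 20% | 11% |
| 20 v 40 | 42% | 30% |
| 30 v 60 | 58% | 45% |

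At 20 v 40, improvers fall from 17.6% to 9.6% on placebo and from 39% to 26% on MitoQ. The t-test has 67% power. If the correlation is 0.81, responder power falls from 62% to 32%.

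Rarer improvers also mean sparser tables. At 20 v 40 the smallest expected count is below 5 in about 71% of trials, against 15% with the plan's cut-off. The chi-squared test then stays slightly conservative (4.4% under the null), and Fisher's test would have 26% power.

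The estimate of s_1 is itself rough. From an assumed 20 placebo participants its 95% sampling range is 0.68 to 1.31 times the true value, which moves the 2.5% rate between 9.0% and 0.5%.

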1. Determine whether Veterans with MS who receive oral MitoQ in comparison to those who receive placebo have less fatigue after a 12-week treatment period as measured by MFIS Score.	Primary Outcome: MFIS Secondary Outcome: FSS	Double-Blind, randomized groups assigned to either 20 or 40 mg of MitoQ or an identical placebo. Check MFIS, and FSS and SDMT at time 0, 6 and 12 wks
2. Determine whether Veterans with MS who receive oral MitoQ in comparison to those who receive placebo, have improved cognitive function, quality of life and depression using SDMT, MSIS-29 and the BDI–FS scores respectively.	Secondary Outcome: SA-EDSS and BDI.	Double-Blind, randomized groups assigned to either 20 or 40 mg of MitoQ or an identical placebo. Check SA-EDSS and BDI at time 0 and 12 weeks
3. Determine the safety and tolerability of MitoQ in subjects with MS using side effects and blood tests.	Secondary Outcome: Safety.	Monitoring of patient response and reporting/recording AEs
4. Determine whether plasma MitoQ levels in Veterans with MS treated with MitoQ correlate with clinical outcomes of fatigue, cognitive function, quality of life, depression, blood inflammatory immune markers, and markers of oxidative stress.	Secondary Outcome: Plasma levels of oral MitoQ 1 hr post-drug. Plasma and/or PBMC IFN- γ , TNF- α , IL-2, IL-6 and IL-17, MDA, HAE, TAC, NOC and SOD	Data collection on MitoQ plasma levels and inflammatory and oxidative stress markers at baseline, week 6 and 12.

Subject Visits and Assessment Schedule

Table 2. Study Activities

	Week 0	Week 1	Week 7	Week 13	
	Visit 1	Visit 2	Visit 3	Visit 4	
Visit time	2 hours	2.5 hours	2.5 hours	2.5 hours	
Purpose	screen, consent	begin treatment	in clinic follow up	end treatment	Total blood draw amount
Consent	X				
Vital signs	X	X	X	X	
Medical history, physical neurological exam	X			X	
T25W, 9HPT, SDMT		X	X	X	
BDI, FSS, MFIS, MSIS-29	X	X	X	X	
Blood testing CBC w/ diff (4mls) CMP (6mls)	X		X	X	30 mls
Blood draw for plasma MitoQ level (4mls)		X	X	X	12 mls
Blood draw for Inflammatory immune markers 40 mls		X	X	X	120 mls
Medication reconciliation	X	X	X	X	
Urine testing (female)	X		X	X	
Side effect monitoring			X	X	

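### The reliable-change cut-off for every patient is scaled by the SD of the control group alone, with no time point given; the baseline SD pooled over all three arms would make it steadier at almost no cost

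*Combined protocol and SAP*

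**What the plan says.** The Data Analysis paragraph under Specific Aim 1 sets out a responder analysis beside the comparisons of means. Reliable change is "defined as differences in group means divided by the standard error", with 1.96 as the cut-off. The standard error is s_1 times the square root of (1 − r_xx), where "s_1 is the standard deviation of the control group" and r_xx is taken from an "alpha value of 0.81". The plan will then "test for differences in the proportion of improvers by group using a chi-squared test". Secondary outcomes are to be handled in the same way.

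The Overall Design table describes "randomized groups assigned to either 20 or 40 mg of MitoQ or an identical placebo", so placebo is the only control group described and is one of three arms. Table 2 has a row for "BDI, FSS, MFIS, MSIS-29" marked at all four visits. Two of these (Visit 1, screening, and Visit 2, start of treatment) come before follow-up on treatment. The plan gives no sample size, allocation ratio or MFIS SD, and does not say at which time point s_1 is measured.

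**The concern.** If the rule is applied to each patient's own change, as a count of improvers requires, the cut-off is 1.96 × s_1 × √(1 − r_xx). Its only data-driven part is s_1. Taken from placebo alone, s_1 rests on about a third of the patients if arms are equal. An unusually small or large placebo SD then moves the cut-off for every patient, and the improver proportions in all arms rise or fall together. An ordinary binomial confidence interval for a proportion does not show this error.

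The missing time point adds a second uncertainty. An SD of scores and an SD of changes give different cut-offs and different levels of the improver rate. What is at stake is the stability and interpretability of the reported proportions.

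**Working it through.** The plan states no cut-off in points and no precision for it, so there is no figure to reproduce.

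**Inputs from the plan:** multiplier 1.96, r_xx = 0.81, three randomised arms, MFIS scheduled before follow-up in all of them.

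**Assumptions:** 10 to 30 per arm (the plan says only that this is a pilot), equal allocation, normal scores, rule applied to each patient's own change, s_1 an SD of baseline scores.

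**Step 1, cut-off.** 1.96 × √(1 − 0.81) = 1.96 × 0.436 = 0.854, so the cut-off is 0.854 × s_1.

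**Step 2, share of information.** At 20 per arm, placebo alone gives 19 degrees of freedom and all 60 patients give 59; 19/59 = 0.32. The relative standard error of an SD is 1/√(2 × df): 1/√38 = 16% against 1/√118 = 9%.

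**Step 3, chance range of the cut-off.** The central 95% range is 0.854 × √(χ²_q/df), with q = 0.025 and 0.975, in units of the true SD.

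| Per arm (assumed) | Placebo only | All arms pooled |
|---|---|---|
| 10 | 0.47 to 1.24 | 0.64 to 1.07 |
| 20 | 0.58 to 1.12 | 0.70 to 1.01 |
| 30 | 0.64 to 1.07 | 0.73 to 0.98 |

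Pooling narrows the range by a little over 40%. Pooling within arms instead of over all patients as one sample gives the same figures at 20 per arm.

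**Step 4, effect on an improver share.** Take a baseline to week-12 correlation of 0.7 and a mean improvement of 0.3 SD (both assumed). The SD of the change is √(2 × 0.3) = 0.775, and the expected share is 1 − Φ((c − 0.3)/0.775). At 20 per arm:
- target c = 0.854: 24%
- placebo only, c = 0.585 to 1.123: 36% down to 14%
- pooled, c = 0.700 to 1.008: 30% down to 18%

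**Step 5, effect on the comparison.** Simulation at 20 per arm, correlation 0.7, improvement of 0.5 SD in both MitoQ arms and none in placebo, MitoQ arms combined against placebo:

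| Quantity | SD, placebo-only s_1 | SD, pooled s_1 | Fall in variance |
|---|---|---|---|
| MitoQ improver proportion | 0.097 | 0.081 | about 30% |
| Placebo improver proportion | 0.085 | 0.079 | 12% to 13% |
| Difference between groups | 0.111 | 0.107 | 6% to 7% |

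The falls are from unrounded SDs and vary slightly between runs. Power is 35% either way, and test size is 4.5% against 4.2%. A three-group chi-squared test at 20 per arm, with correlation 0.81 and effects of 0, 0.25 and 0.5 SD, gives power of 29.2% either way and size of 3.8% against 3.9%.

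**Step 6, effect of the unstated time point.** In the Step 5 setting, taking s_1 as the placebo SD of change scores gives a mean MitoQ improver share of about 42%. The pooled baseline SD gives about 33%.

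**The case against.** The strongest objection is that the plan never calls s_1 a baseline SD. The same paragraph plans SDs both for each measure and for its change, and randomisation equalises SDs across arms only before treatment. If a week-12 or change SD was intended, pooling baseline data substitutes a different quantity. This stands, and Step 6 shows that it can move the improver rate by about nine percentage points. It is a reason to name the time point. It does not rescue the present wording, because a score's standard error built from a reliability coefficient needs an SD of scores.

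A second objection is that the sentence has larger faults. A ratio of group means cannot classify a patient, and s_1 × √(1 − r_xx) is the error of one score, not of a difference (0.854 against 1.208 SD). This is true, but correcting both would leave the rule scaled by one arm's SD. The relative chance range of s_1 at 20 per arm (0.69 to 1.31 placebo only, 0.82 to 1.18 pooled) does not depend on the multiplier.

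Three stronger readings are tempting and should be resisted:
- *The placebo SD distorts the treatment comparison.* All arms share the cut-off, and in the checks above test size stays below 5% and power does not move.
- *The improver proportions will size the next trial.* The paragraph's remark about planning data may refer to the mixed model, and the Aim 1 procedures base sample-size planning on the mean, SD and confidence interval of the MFIS change.
- *The arm is known to be small.* The plan says only that the trial is a pilot.

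**Conclusion.** The point holds as a minor refinement. The cut-off rests on one arm's SD with no time point named, while baseline MFIS from all arms would estimate an SD of scores with about three times the information if arms are equal. The gain is mainly in the stability of the reported improver proportions, chiefly in the MitoQ group. It is small for the between-group difference and practically nil for test size and power. The sizes rest on assumed arm sizes, equal allocation, normal scores and, for the simulated proportions, an assumed correlation and effect. The documents do not support reading this as a threat to the validity of the comparison.

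**What to change.** In the Specific Aim 1 data analysis, define s_1 as the SD of total MFIS at the Visit 2 (start of treatment) assessment, completed before the first dose and pooled over all randomised patients. Naming the visit matters because Table 2 schedules MFIS at both Visit 1 and Visit 2. Apply the single resulting cut-off to each patient's own change. For each secondary scale analysed in the same manner, use that scale's own pooled baseline SD.

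In the same edit, replace the ratio of group means with the patient's change and use the standard error of a difference; pooling alone cures neither.

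The cost is a short wording change, with no new data and no material loss of power. The one downside is that, if the sponsor meant a week-12 or change-score SD, the level of the improver rates will change. The sponsor should confirm the intended quantity when making the edit.

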Specific Aim 1: Determine whether Veterans with MS who receive oral MitoQ in comparison to those who receive placebo have less fatigue after a 12-week treatment period as measured by MFIS Score. Our hypothesis is that MitoQ preserves or improves the mitochondrial function and that in turn may improve fatigue in MS therefore MS veterans taking MitoQ will have less fatigue than those Veterans with MS taking placebo.

Introduction: Fatigue, a common MS symptom can be a cause of significant disability, and loss in quality of life in Veterans with MS. While the mechanisms responsible for fatigue in MS are poorly understood it is possible that reversible mitochondrial dysfunction due to oxidative stress and resultant neuronal ATP depletion may contribute to fatigue. Orally administered MitoQ is a mitochondria-targeted antioxidant similar to CoQ10 but more effective in migration to mitochondria compared to CoQ10 and is aimed at reducing the effects of mitochondria-derived ROS, which lead to mitochondrial dysfunction. While a pilot study using CoQ10 for fatigue improvement in MS showed positive results, studies evaluating effects of oral MitoQ in MS have not been conducted.

Procedures: We will determine the effects of 20 or 40 mg oral MitoQ versus placebo on MS fatigue as measured by MFIS. We will obtain descriptive information about changes in MFIS scores for each subject group and will use the collected data to determine the mean, SD, and confidence interval of this change. This information will also help determine sample size and power analysis for a future phase II trial. This study will be the first to assess whether MitoQ changes fatigue in MS subjects. Data from MFIS scores taken at baseline assessment, and 6- and 12-week time points will be assessed, to determine changes in MFIS fatigue scores. The primary outcome measure will be the change from baseline total MFIS score to 12-week total MFIS score. Secondary outcome measures will be the change from baseline to each of the following measures: 6-week MFIS and 6 and 12-week FSS scores.

Statistical Analysis

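### The power gain credited to the improver chi-squared test is wrong in direction: under the t-test's own model, splitting MFIS change loses at least 36% of the information

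*Combined protocol and SAP*

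**What the plan says.** All the text at issue is in the Data Analysis paragraph of Specific Aim 1, except the endpoint, which is in the Procedures paragraph just before it.

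- Endpoint: "The primary outcome measure will be the change from baseline total MFIS score to 12-week total MFIS score".
- Reference test: "We will conduct a t-test to compare primary and secondary measures (changes from baseline").
- Improver analysis: "we will categorize participants who improved by a reliable change, defined as differences in group means divided by the standard error", with the threshold and test given as "greater than 1.96 points and test for differences in the proportion of improvers by group using a chi-squared test".
- Standard error for the cut-off: s1√(1 − r_xx), where "s_1 is the standard deviation of the control group" and r_xx is taken from an "alpha value of 0.81".
- The next sentence: "This analysis will yield additional power (compared to a 2-sample t-test"). It goes on to say that the analysis will supply useful data for planning a repeated-measures analysis in a later, larger trial.

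The linear mixed model comes several sentences earlier. Between it and the power claim stand the rationale for the 6-week time point, the dose-trend ANOVA and the improver test. The plan gives no sample size, SD, effect size or calculation in support of the claim.

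**The concern.** Read where it stands, the power claim refers to the improver analysis. It then says that a yes/no version of the primary endpoint is more sensitive than a t-test on the same endpoint kept continuous. Under the model that the t-test assumes, the reverse is true, because the split discards how far each patient lies from the cut-off.

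What is at stake is interpretation. A reader who takes the sentence at face value would give a non-significant improver comparison more weight than it can bear, as though it came from the stronger test. The paragraph also says that the secondary outcomes will be analysed in the same way, so the claim may be carried over to FSS and the other scales.

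**Working it through.** The plan states no power figure that could be reproduced, so the check is of the direction of the claim and the size of the loss.

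**Inputs from the plan.** Multiplier 1.96; r_xx = 0.81; s1 = control-group SD, with no value given and no statement of whether it is the SD of scores or of changes; significance at P < 0.05.

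**Assumptions, because the plan is silent.** Normal changes with a shift in mean; a two-sided test; two groups of equal size; effects of d = 0.5 or 0.8 SDs of change. The definition of reliable change is written in terms of group means, which cannot classify individuals. It is therefore read as individual improvement divided by the standard error, greater than 1.96.

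**Step 1: bound for any cut-off.** With the cut at c SDs of change, the information kept relative to the t-test (small-effect limit) is φ(c)² / [Φ(c)(1 − Φ(c))]. The maximum is at c = 0, where it equals 2/π = 0.637. The loss is therefore at least 1 − 0.637 = 36%.

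**Step 2: the plan's cut-off.** √(1 − 0.81) = 0.436, and 1.96 × 0.436 = 0.854, so the cut is 0.854 s1.
- If s1 is the SD of change, c = 0.854.
- If s1 is the SD of scores and the baseline-to-week-12 correlation is ρ, the SD of change is s1√(2(1 − ρ)), and c = 0.854/√(2(1 − ρ)). At ρ = 0.5 this is again 0.854. At ρ = 0.81 it is 0.854/0.616 = 1.386.

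**Step 3: information lost at that cut-off.** A mean placebo improvement, in SDs of change, is subtracted from c.

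| ρ (assumed) | c | Loss, no placebo change | Placebo +0.3 SD | Placebo +0.5 SD |
|---|---|---|---|---|
| 0.3 | 0.722 | 47% | 40% | 37% |
| 0.5 | 0.854 | 51% | 43% | 39% |
| 0.7 | 1.103 | 60% | 50% | 44% |
| 0.81 | 1.386 | 69% | 59% | 52% |

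**Step 4: patients per arm for 80% power, no placebo change.** For the t-test (normal approximation), n = 2(1.96 + 0.842)²/d², which gives 63 at d = 0.5 and 25 at d = 0.8. For the proportions, n = [1.96√(2p̄q̄) + 0.842√(p0q0 + p1q1)]²/(p1 − p0)², with p0 = 1 − Φ(c) and p1 = 1 − Φ(c − d).
- c = 0.854, d = 0.5: p0 = 0.196, p1 = 0.362, n = 115, ratio 115/63 = 1.83. With 63 per arm the power is 54%.
- c = 0.854, d = 0.8: p1 = 0.478, n = 43, ratio 43/25 = 1.72. With 25 per arm the power is 56%.
- c = 1.386, d = 0.5: p0 = 0.083, p1 = 0.188, n = 166, ratio 166/63 = 2.63. With 63 per arm the power is 41%.
- c = 1.386, d = 0.8: p1 = 0.279, n = 60, ratio 60/25 = 2.40. With 25 per arm the power is 44%.

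Even the best cut-off needs 100 against 63 per arm at d = 0.5, and 40 against 25 at d = 0.8.

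**Step 5: small-sample check.** In a simulation of 20,000 normal trials per case, with 20 per arm and d = 0.8, the t-test had power of 0.69 to 0.70. The uncorrected chi-squared test had 0.49 at c = 0.854 and 0.36 at c = 1.386.

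**The case against.** The best defence is that the sentence is merely in the wrong place. A responder proportion at a single time point does little to plan a repeated-measures analysis. The mixed model in the same paragraph does, and it is the usual source of a power gain over a two-sample t-test. This reading is plausible and probably correct. It explains the error but does not remove it: where the sentence stands, it attaches to the improver test, and the text needs changing on either reading.

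A second defence is that the loss depends on the model. In simulation, a 30% subgroup improving by 2 SDs, with the cut at 1.386 and 20 per arm, gave the chi-squared test 0.36 against 0.335 for the t-test. Heavy-tailed changes (t with 3 degrees of freedom) could also bring the two level, or put the chi-squared test slightly ahead, when the cut was near the centre. This stands as a limit on generality. The plan invokes no such model, and its claim is unconditional.

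A third defence is that the improver test is an addition, while the plan puts its weight on confidence intervals for the difference in mean change. That is right, and it limits the harm. A reader might infer that the future trial would be sized on the weaker improver endpoint. The documents do not support that: the Aim 1 Procedures tie future sample size to the mean, SD and confidence interval of MFIS change. Nor do they require the improver comparison to be purely descriptive. A supportive test is acceptable in an exploratory pilot, provided no power gain is claimed for it.

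**Conclusion.** Wrong as written. At its present place the sentence gives the improver chi-squared test a power advantage that it does not have under the t-test's model. The firm figure is a loss of at least 36% of the information at any cut-off, assuming normality and a shift in mean. At the plan's cut-off, as interpreted above, the loss is about 51% to 69% with no mean placebo change and correlations of 0.5 to 0.81. In the cases worked in Step 4 this means about 1.7 to 2.6 times as many patients for equal power.

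A reader might infer that half or more of the information is always lost. The documents do not support that: they give no SD, correlation or expected placebo change. With placebo improvement or a correlation of 0.3, the loss can fall to about 37% to 50%, although at a correlation of 0.81 it stays above half even with a placebo improvement of 0.5 SD. The primary t-test and its confidence interval are unaffected.

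**What to change.** Delete the power claim from the improver analysis. If it was meant for the baseline-adjusted linear mixed model or the ANCOVA, move it there, name the analysis, and give the reason for expecting a gain (for example, an assumed correlation between baseline and follow-up).

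Add one sentence stating that the improver comparison is supportive, that it is expected to have less power than the continuous MFIS analyses, and that a null improver result is not evidence against an effect on mean MFIS change.

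The cost is a sentence or two of wording and a less favourable claim. No data, visits or primary analyses change.
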